Surgical procedure or Specimen removal during surgery				
Tissue banking (complete Section 12)				
Use of pre-existing tissues/specimens				
Other (list):				

- **Standard of care procedures are procedures performed in the course of normal medical care.*
- ***Research Procedures are performed for the purposes of this research alone.*

13. Please describe the research design and all study related procedures.

- Describe ALL PROCEDURES ASSOCIATED WITH THIS RESEARCH. This includes standard of care and research procedures.
- For complex studies please include diagrams and tables. Be sure to describe when each procedure will be performed. Be sure to provide information for each cohort, including normal controls.

Study participants based on the inclusion and exclusion criteria listed below will be recruited from the Oncology clinics and medical services of the Cleveland VA. The study oncologist will review the study with them. Subjects that consent will be randomized to one of the two arms, vaccine or no vaccine. Individuals will undergo blood draws for immunologic assays according to time points depicted in the figure below. Each blood draw (25 ml each) has been timed to follow routine clinical monitoring as ordered by the oncologist for maximum feasibility.

- The first blood draw will be at the time of consent into the study. We anticipate this time to be the first visit with the oncologist. They will receive ZOSTAVAX on that day if they are in that arm of the study.
- The second blood draw will be on the day of chemotherapy initiation, no earlier than 14 days post-vaccination. This will be longer than 14 days for example when there is surgery between the vaccination and the start of chemotherapy.
- The third blood draw will be at the start of the second chemotherapy cycle.
- The fourth blood draw will be 3-24 months post chemotherapy cessation. The timing of the final blood draw is based on cessation of chemotherapy and not any concurrent radiation therapy that would be also completed by the 3-6 month post-chemotherapy sampling.

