The subjects chemotherapy is decided by the Oncologist and/or Tumor Board in consultation. The duration of chemo similarly is also decided clinically. If the patient needs surgery or XRT

as part of the therapy, it is decided on entirely by the clinicians. The study is working around all of these clinical decisions.

Subjects will be called between visit 2 and 3 and then between visits 3 and 4. They will be asked if they had a side effects or event that may have been serious since the last study visit or telephone contact. They will also be asked if they were exposed to anyone who has chickenpox or shingles, and if they had any symptoms of shingles.

For 4 weeks after they receive their shot, they will be asked to record information about potential vaccine side effects on the vaccination Report Card.

14. Will the research involve the following?

N/A Chart/Data Review

Placebo Group No Yes (describe):

Other Control Group No Yes (describe): The control group is persons that do not get the vaccine.

Randomization No Yes (describe): We will obtain clinical information to determine eligibility this includes meds and PMH and then follow the subject's clinical course to know when to do the subsequent sampling. We will use a cloud based randomized tool to generate the list before the start for the whole study for what the order of vaccine or no vaccine will be. We will then have paperwork packets in the order of enrollment premade. We will open each packet at the consenting time and find vaccine or not and enroll and begin the study.

Deception No Yes (describe):

15. Does the research involve the use and/or disclosure of Individually Identifiable Health Information in any form or medium?

No Yes If yes, complete the required HIPAA Waiver/Authorization forms.

16. Does the study include the administration of a study agent that does not require FDA approval and does not require an IND (e.g. vitamins, food supplements, isotope tracers, alternative medicines, etc.)?

No Yes -provide a detailed description of the procedures used to assure patient safety:

17. Will radioactive material be administered or will subjects be exposed to ionizing radiation?

• Ex. Radiographic equipment, fluoroscopic equipment, and CT scanners, etc.

No Yes

18. In your judgment, could the objectives of the research be met in a way that presents less risk to subjects?

No Yes please explain:

Section 4 – Subject Selection, Recruitment, and Vulnerable Populations

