Safety and tolerability will be assessed by statistical and clinical review of all safety data collected throughout the study. All subjects who are vaccinated and provide any safety follow-up will be included in safety analyses and summaries. To provide an overall assessment, the incidence rate for the vaccination group and no-vaccination group, the risk difference between the two groups and the associated 95% CI will be provided for broader safety measures such as the proportions of the subjects with any: adverse experiences; injection-site adverse experiences; systemic adverse experiences; serious adverse experiences; or vaccine-related serious adverse experiences after vaccination.

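### Safety contacts are timed by chemotherapy and only the vaccine arm keeps a report card, so the between-arm safety comparison rests on unequal collection

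*Protocol*

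**What the plan says.** Protocol item 13 draws the first blood sample at consent and gives the vaccine that day to those allocated to it. The later draws follow chemotherapy:

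- Visit 2: "The second blood draw will be on the day of chemotherapy initiation, no earlier than 14 days post-vaccination". The item adds that the gap is longer when surgery comes first.
- Visit 3: "The third blood draw will be at the start of the second chemotherapy cycle".
- Visit 4: "The fourth blood draw will be 3-24 months post chemotherapy cessation".

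(Item 13 numbers the blood draws, not the visits. I read visit 2 as draw 2, and so on.)

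The calls are set by these visits: "Subjects will be called between visit 2 and 3 and then between visits 3 and 4". Their content is: "They will be asked if they had a side effects or event that may have been serious since the last study visit or telephone contact". Callers also ask about exposure to chickenpox or shingles and about shingles symptoms.

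The report card is for vaccinated subjects: "For 4 weeks after they receive their shot, they will be asked to record information about potential vaccine side effects on the vaccination Report Card".

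SAP 2.7 defines who is analysed for safety: "All subjects who are vaccinated and provide any safety follow-up will be included in safety analyses and summaries". It then promises incidence in both the vaccinated and unvaccinated groups, with a risk difference and 95% confidence interval, for several adverse-experience categories including serious ones.

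**The concern.** Hypothesis 5 in Protocol item 9 is that the vaccine is safe when given before chemotherapy, or before surgery followed by chemotherapy. The test of it is a comparison with unvaccinated controls, which needs events to be sought in the same way and over the same time in both arms.

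The contacts as written depend on how the cancer treatment proceeds, and in the first weeks they also depend on the arm. The interval from day 0 to visit 2 includes the early weeks after a live attenuated vaccine and any surgery. In that interval vaccinated subjects have a card and controls have nothing scheduled. A difference in recorded events could then reflect who was asked. Events that were not collected at the time may not be recoverable at analysis.

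**Working it through.** The plan gives no adverse-event rate, no expected loss to safety follow-up and no precision for the safety comparison, so there is no figure to reproduce. The check traces subject paths through item 13 and then shows how large an error could be under stated assumptions.

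**Paths**

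| Path | Scheduled calls | Card | Other scheduled visits |
|---|---|---|---|
| Never starts, vaccinated | None | 4 weeks | None after visit 1 |
| Never starts, control | None | None | None after visit 1 |
| Stops in cycle 1 | Visit 3 is missing, so the first window has no end and the second no start | Vaccinated only | Visit 4 still due |
| Stops after cycle 2 starts | Both windows exist | Vaccinated only | Visit 4 due |
| Completes, surgery first | Both, but none before visit 2 | Vaccinated only; may end before visit 2 | All |

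The first call looks back only to the last visit or contact. Read literally, for a subject who reached visit 2 it does not cover day 0 to visit 2.

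**Size of error in one arm**

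Let N be the arm size, m the number with no safety follow-up, p the event proportion among those followed, and R the risk in the unfollowed relative to the followed. If the unfollowed are left out:

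- reported proportion = p
- true proportion = [(N − m)p + mRp] / N
- bias = reported − true = −(m/N) × p × (R − 1)

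Inputs: N = 30 + 15 = 45 (Protocol items 20 and 21). The values of m, p and R are assumptions. For scale only, m = 7 is close to 45 × 0.15 = 6.75, using the loss that SAP 2.7 allows for the immune analysis; it is not a safety-loss rate.

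| m | p | R = 0.5 | R = 1 | R = 2 | R = 3 |
|---|---|---|---|---|---|
| 7 | 20% | +1.6 | 0 | −3.1 | −6.2 |
| 2 | 20% | +0.4 | 0 | −0.9 | −1.8 |
| 7 | 10% | +0.8 | 0 | −1.6 | −3.1 |
| 2 | 10% | +0.2 | 0 | −0.4 | −0.9 |

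(Bias in percentage points. Example: −(7/45) × 0.20 × (3 − 1) = −0.062.)

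**Effect on the risk difference (vaccine minus control)**

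With m = 7 and p = 20%, loss confined to controls shifts the risk difference by −1.6 to +6.2 points as R runs from 0.5 to 3. Loss confined to the vaccine arm shifts it by +1.6 to −6.2. Identical loss in both arms cancels. A second mechanism is separate: a control who stays in the denominator but is never asked about day 0 to visit 2 is recorded as event-free for that interval, which pushes the difference upward.

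**Counting the unfollowed as event-free**

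With m = 7 and p = 20%, the observed events are 38 × 0.20 = 7.6. Putting all 45 in the denominator gives 7.6/45 = 16.9%. The true value runs from (7.6 + 0.7)/45 = 18.4% at R = 0.5 to (7.6 + 4.2)/45 = 26.2% at R = 3. So 16.9% is too low in every case. A range from none to all of the 7 having an event is 16.9% to (7.6 + 7)/45 = 32.4%.

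**The case against.** **The calls are not the only source.** SAP 2.7 reviews all safety data collected. The card does not depend on chemotherapy, and a returned card is enough to keep a vaccinated subject in the safety set. Item 63 has both sites review the study and the cards at least monthly. Item 12 ticks retrospective chart review, and item 54 notes that the oncology co-investigators treat the subjects. This stands against any claim that never-starters are automatically excluded. It does not close the gap. Controls have no card, chart review is given no safety purpose or schedule, and item 14 follows the clinical course in order to time the sampling.

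**Visits may include an adverse-event enquiry.** The call question refers back to the last visit, which suggests that events are asked about there. If so, subjects in both arms who reach visit 2 are covered by recall. The documents do not say this, and it would not help subjects who have no visit 2.

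**The number affected may be small.** This is a pilot in patients with planned chemotherapy, and no never-starter rate is given. That is fair, and it is why the size above is only illustrative.

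**Stronger readings that do not hold.** A reader might infer that anyone who stops chemotherapy gets no call. The documents do not support this: cessation triggers visit 4, and stopping after cycle 2 starts leaves both windows intact. A reader might also infer that events must be understated. Removal conditions in item 65 include serious adverse events and worsening, so higher risk among those lost is plausible, but the documents do not establish it. With equal risk the bias from leaving out the unfollowed is zero, and with lower risk it reverses.

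**Conclusion.** The point holds in a limited form. Both calls depend on chemotherapy-defined visits with no fallback, so a never-starter has no scheduled call, and for a subject who stops in cycle 1 the windows are undefined. Between day 0 and visit 2 the scheduled collection differs by arm, and a never-starter control has none. The inclusion sentence in SAP 2.7 does not define the control denominator that its own risk difference requires.

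The direction and size of the bias cannot be fixed from the documents. Under the assumptions shown, the error in one arm lies between +1.6 and −6.2 points with 7 of 45 unfollowed, and between +0.4 and −1.8 with 2 of 45, at 20% incidence among those followed. The conclusion rests on reading item 13 as the complete schedule of safety contacts. The card itself is not in the documents, so its return instructions are unknown.

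**What to change.** **Protocol item 13**

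- Make a safety contact in both arms at the end of the 4-week card period, counted from day 0, whether or not visit 2 has occurred. Ask about events since day 0, and collect the card from vaccinated subjects. Where this date falls between visits 2 and 3, it can serve as the first planned call.
- Give the later call a fallback calendar date for use when visit 3 or visit 4 does not occur. Apply it to every randomised subject, including those who never start chemotherapy.

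**SAP 2.7**

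- Define the safety set for both arms.
- Report, by arm, the number with no safety follow-up.
- Show a sensitivity range for those subjects. Do not count them as event-free in the denominator, since that lowers the reported incidence without any added information.

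**Cost.** Some calls must be scheduled by date and not around clinic visits, and subjects who have surgery first may need one extra call. The SAP change is a few sentences and a line in the safety table.

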2. We hypothesize that the fold increase in Varicella Zoster Virus (VZV)-specific immunity in subjects with solid organ tumors that were given ZOSTAVAX at least 14 days prior to initiation of chemotherapy will be higher than the control group that is not vaccinated.
3. We hypothesize that immediately before the second cycle of chemotherapy VZV-specific immunity will be higher in those subjects that received ZOSTAVAX prior to chemotherapy than those that were not vaccinated.
4. We hypothesize that at 3-18 months post-chemotherapy VZV-specific immunity will be higher in those subjects that received ZOSTAVAX prior to chemotherapy than those that were not vaccinated.
5. We hypothesize that ZOSTAVAX is safe if given to subjects with solid organs tumors at least 14 days prior to initiation of chemotherapy or surgery followed by chemotherapy.

10. Describe the means of analyzing the data and evaluating the results.

- *State the anticipated methods to be used for analysis and interpretation of the data.*
- *The methods must compliment the design of the study and the nature of the data which is being collected.*

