No Yes- explicitly describe your process for identifying and/or recruiting these patients: (address all cohorts): See the answer for question 27. We will focus on subjects with recent cancer diagnosis that will be seen in the clinics of oncology or by their inpatient team. We can assist the oncologists in prescreening for suitability to the study. Also the coordinator and Co-I may discuss with the medical teams about our study that we are searching for subjects with oncology diagnosis that will receive chemo soon and the primary providers then may refer subjects to us to screen.

29. In addition to the consent form will any other materials be given to the subject?

N/A Chart/data review

No Yes- check all that apply and submit for IRB review:

Letter

Information Sheets

Questionnaire, Survey, Diary

Other (flyer, brochure, describe): If they enroll they will fill out the vaccine report card.

30. Please list by bullet point inclusion/exclusion criteria for the study.

- *Entry criteria should be as detailed as necessary to define the subject population(s) under study and reduce confounding design. Include precise criteria for age, gender, and other relevant factors.*
- *List specific exclusion criteria which could interfere with the study design or place a subject at risk during the study.*
- *Provide answers for each cohort, including normal controls.*

Inclusion criteria:

- Solid organ tumor patients that have at least 14 days between entry into the study with ZOSTAVAX vaccination and initial therapy for their malignancy that will include chemotherapy alone or surgery with subsequent chemotherapy plus or minus radiation therapy.
- A plan for chemotherapy that at the onset at least has an anticipated stop date within 3-6 months of our sample collection phase of the study.
- Age 50 or older

Exclusion criteria:

- Prior history of HZ or shingles vaccine
- Systemic chemotherapy <3 months prior to enrollment
- Any history of hematologic malignancy, HIV/AIDS, hematopoietic stem cell transplant, or other cellular immunodeficiency state
- Those receiving immunomodulating drugs at the time of vaccination such as prednisone, methotrexate, azathioprine, mercaptopurine, or other biologics including TNF- α inhibitors
- Widespread metastatic tumor with bone marrow involvement
- Indefinite duration palliative chemotherapy subjects
 - Inability to communicate with the study staff or being unable to consent for themselves.

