****If yes complete the following:**

a. The LSCDVAMC investigator will send:

- Hardcopy information or specimens
 Electronic information

b. What are the procedures for transporting and/or transmitting identifiable information securely?

c. What will be the final disposition of the identifiable data transferred offsite?

- Record Control Schedule 10-1 indicates that all research records must be retained indefinitely

Records will be maintained indefinitely or until the RCS-10 is updated.

62. Record Control Schedule 10-1 indicates all research records must be retained indefinitely. Please indicate where this information will be stored and the safe guards to protect it:

a. Electronic Safeguards:

- No electronic data will be stored
 VA encrypted laptop
 Encrypted VA device/media- describe:

- VA network drive;
 - M: drive; whose?
 - S: drive
 - Folder access password protected
 - Other drive location (for example P: drive):
 - Folder access password protected

b. Hardcopy safeguards. Two locking barriers must be in place.

- No hardcopy data will be stored
- Locked Office and Locked File Cabinet
- Coded by Study Staff
- De-identified by Privacy Officer or Statistician
- Other- Describe:

Facility name, address, and room number where hardcopy or electronic data will be stored:

For long term storage the paper will go to Wade Park VA, K203, [name] in a locked cabinet in [name] laboratory.

Section 8 – Data and Safety Monitoring – Greater than Minimal Risk Study

- For all research that is greater than minimal risk a Data and Safety Monitoring Plan must be developed.
- This is a plan to assure the research includes a system of appropriate oversight and monitoring of the conduct of the study to ensure the safety of subjects and the validity and integrity of the data.

*CHECK BOX IF THIS IS A MINIMAL RISK STUDY SKIP TO #65

63. Safety monitoring for this greater than minimal risk project will include:

- Data Safety Monitoring Board:
- Data Monitoring Committee
- Other

- *Attach the plan or provide details including whether committee is independent from the study sponsor, how often it meets, whether written reports are available, etc*

The PI, primary Co-I's, and Coordinators of the study (Cleveland and Duke) will correspond at least monthly and review the study and vaccine report cards for any sign of increased toxicity in this population.

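### The Report Card ends 4 weeks after the shot and can close before chemotherapy starts; two loosely worded calls then carry the safety follow-up, and the SAP does not separate the two periods

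*Protocol*

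**What the plan says.** **Hypothesis (Protocol item 9, Hypothesis 5).** The claim to be supported reads: "ZOSTAVAX is safe if given to subjects with solid organs tumors at least 14 days prior to initiation of chemotherapy or surgery followed by chemotherapy". Item 44 describes the product as a live attenuated virus vaccine.

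**Report Card (item 13).** "For 4 weeks after they receive their shot, they will be asked to record information about potential vaccine side effects on the vaccination Report Card". The card itself is not reproduced, so its items and how often it is filled in are unknown.

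**Start of chemotherapy (item 13).** "The second blood draw will be on the day of chemotherapy initiation, no earlier than 14 days post-vaccination". The text continues: "This will be longer than 14 days for example when there is surgery between the vaccination and the start of chemotherapy". No upper limit is given. The inclusion criterion in item 30 requires "at least 14 days between entry into the study with ZOSTAVAX vaccination and initial therapy for their malignancy", which for surgery-first subjects reads as 14 days to surgery, with chemotherapy later.

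**Telephone calls (item 13).** All subjects are called once between visits 2 and 3 and once between visits 3 and 4. The question covers side effects or a possibly serious event since the previous visit or call. Exposure to chickenpox or shingles and symptoms of shingles are asked about separately.

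**Oversight (item 63).** At least monthly, the study teams are to "review the study and vaccine report cards for any sign of increased toxicity in this population".

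**Analysis (SAP section 2.7).** Safety data from the whole study are summarised as incidence by arm and risk difference with 95% CI. The list of measures runs from any adverse experience to the last category, "or vaccine-related serious adverse experiences after vaccination". Chemotherapy start is not used as a dividing point.

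**The concern.** What is specific to this population is how a live vaccine behaves once immunosuppressive treatment follows it. The one structured instrument is timed from the shot, whereas the exposure named in Hypothesis 5 is timed from chemotherapy. The two windows overlap briefly or not at all, and the overlap is shortest for surgery-first subjects, a group that the hypothesis names.

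Two things are at stake. First, non-serious events under chemotherapy may be collected less completely, or differently from one caller to the next, than events in the weeks after the shot. Second, a single pooled figure does not show which period it describes. A reassuring overall risk difference could be cited for safety under chemotherapy without showing how much of the evidence came from that time.

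**Working it through.** The plan gives no figure on this point to reproduce. The check is a timeline.

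**Inputs**
- Card length: 28 days from the shot (item 13).
- *c* = days from vaccination to chemotherapy start: 14 or more, no maximum (item 13). Values of *c* above 14 below are assumptions.
- Visit numbers are taken to match the blood-draw numbers in item 13, so visit 2 is the day chemotherapy starts and visit 3 the start of cycle 2.

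**Formulas**
- Card days on or after chemotherapy start = max(0, 28 − *c*)
- Days from end of card to visit 2 = max(0, *c* − 28)

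| *c* (day chemotherapy starts) | Card days on chemotherapy | Days from card end to visit 2 |
|---|---|---|
| 14 | 28 − 14 = 14 | 0 |
| 21 | 28 − 21 = 7 | 0 |
| 28 | 0 | 0 |
| 35 | 0 | 35 − 28 = 7 |
| 42 | 0 | 42 − 28 = 14 |
| 56 | 0 | 56 − 28 = 28 |

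**Surgery-first subjects.** If surgery takes place no earlier than day 14 and chemotherapy follows *s* days later, then *c* is at least 14 + *s*, and the card covers at most max(0, 14 − *s*) days on chemotherapy. That is zero once *s* is 14 or more. The documents give neither *s* nor the proportion of surgery-first subjects.

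**What the calls add**
1. Call 1 falls within cycle 1 and looks back to the last visit or call, which is visit 2. It does not reach behind visit 2.
2. No call is planned between visits 1 and 2, and no safety questions at visit 2 are described. When *c* exceeds 28, the days in the last column have no described prompt.
3. Call 2 is a single contact in an interval that runs from the start of cycle 2 to a draw 3 to 24 months after chemotherapy ends. No safety questions at visits 3 or 4 are described.
4. The general question can be read in two ways: any side effect, or else a possibly serious event; or only side effects and events that may have been serious. Item 38 lists fever and a chickenpox-like rash among the vaccine's risks. The call description names neither, although it does name shingles symptoms.

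**Control arm.** Item 13 ties the card to the shot, whereas item 29 says without limit of arm that enrolled subjects complete it. It is therefore unclear whether controls have a card, although the SAP plans risk differences between the arms.

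**What period tables can show.** With 90 enrolled, each arm has 45. If no events are seen, the upper limit of the exact two-sided 95% interval is 1 − 0.025^(1/45) = 7.9%. In a subgroup of 22 (assumed, about half an arm) it is 1 − 0.025^(1/22) = 15.4%.

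**The case against.** The strongest reply is that safety follow-up does not end with the card. Both calls come after chemotherapy starts, reach every subject including those with surgery first, and ask directly about shingles symptoms, perhaps the most relevant late event. Oncology co-investigators treat the subjects (item 54), staff follow the clinical course (item 14), chart review is a listed procedure (item 12), and the monthly review covers the study as well as the cards. The SAP uses safety data from the whole study. This stands, and it rules out several stronger readings that a reader might infer:

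- *That solicited safety collection stops at week 4.* It does not; only the card stops.
- *That non-serious events on chemotherapy are not asked about.* The wording is ambiguous and one reading includes them.
- *That the overall comparison is dominated by days before chemotherapy.* Nothing in the documents allows this to be calculated, and follow-up extends well beyond chemotherapy.
- *That Hypothesis 5 should rest on the chemotherapy period alone.* That would set aside the acute period after vaccination, which the hypothesis also covers and for which the SAP lists injection-site events.

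It is also fair to say that period tables in an open-label pilot of this size will be imprecise, and that self-reports in an unvaccinated arm are open to reporting bias.

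The reply does not close the gap. The clinical sources are not described as a systematic count of adverse events, the call wording remains open to two readings, and an analysis of all the data cannot restore events that nobody asked about.

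**Conclusion.** The concern holds in a limited form. Structured card recording covers at most 14 days of chemotherapy and none if it starts on day 28 or later. The two calls are then the only prompted safety collection described, and their question does not settle whether non-serious events count. For a start after day 28, the interval from card end to visit 2 has no described prompt. The SAP offers no view of the period before chemotherapy separately from the period after it.

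The 14-day maximum follows directly from the protocol. How many subjects have little or no card coverage depends on the surgery-first share and the interval from surgery to chemotherapy, neither of which is stated. The conclusion also assumes that no safety questions are put at visits 2 to 4 beyond those the documents describe. This is a weakness in how well the trial can answer Hypothesis 5. It does not show that harms will be missed, and it does not affect the immunological analyses.

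**What to change.** **(a) SAP section 2.7.** Alongside the overall figures, report incidence and risk difference with 95% CI for two periods: day 0 to chemotherapy start, and chemotherapy start onward. Assign events by onset date. Draws 1 and 2 mark these boundaries in both arms. State the denominator for the second period (subjects who start chemotherapy). Interpret Hypothesis 5 on both periods, and keep any surgery-first split descriptive.

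**(b) Protocol item 13.** Word the call script to ask about any adverse event, naming fever and any rash, as well as the existing exposure and shingles questions. Ask the same questions at draws 2, 3 and 4 in both arms. At draw 2 the questions should look back over the time since the card ended, which closes the gap before visit 2.

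**Optional.** A second card from chemotherapy start, given to both arms and added to the monthly review. It adds burden and is not essential if (a) and (b) are done.

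**Cost.** Contacts that already exist become slightly longer, more chemotherapy-related events are recorded, and the period tables will be sparse and mainly descriptive. The unblinded comparison remains open to reporting bias. No treatment or vaccination rule changes.
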